Effect of Whole Body Vibration Therapy on Muscle Function, Gross Motor Function and Bone Mineral Density in Children with Spinal Muscular Atrophy - a Feasibility Study

NCT number: NCT03056144

Document date: August 1, 2018

Effect of Whole Body Vibration Therapy on Muscle Function, Gross Motor Function and Bone Mineral Density in Children with Spinal Muscular Atrophy - a Feasibility Study

Abstract

Spinal muscular atrophy (SMA) are one of the common physical disabilities in childhood. For SMA, progressive muscle weakness and early fatigue hamper the mobility of the sufferers. Osteopenia is common for this population group due to poor bone growth and muscle disuse. As a result, non-traumatic related fractures and bone pain are common. Recently, whole body vibration therapy (WBVT) has been proven to improve bone health and muscle function in healthy adults and post-menopausal women. Among the limited studies on the WBVT for children with muscular dystrophies, promising results have been shown on gross motor function, balance, and muscle strength and the WBVT appears to be safe for children with SMA.

The present pilot study is designed to investigate if WBVT is safe and feasible for individuals with SMA and if WBVT can improve muscle function, functional abilities, postural control and bone mineral density in children with SMA. Convenience samples of 10 individuals with SMA type III will be recruited. The participants will receive the WBVT of 25 Hertz and a peak-to-peak amplitude of 4mm for a session of about 18 minutes, 3 days per week for 4 weeks. Assessment will be performed at the baseline and the completion of the intervention to examine the muscle function, functional abilities, postural control and bone mineral density of the participants.

It is anticipated that the outcomes of this pilot study for SMA may show if this intervention is safe, feasible and beneficial for children with SMA type III regarding to muscle function, functional abilities, postural control and bone mineral content and if there may be any related practical issues of this intervention to this population group. The outcomes also provide research evidence to clinicians if this intervention should be recommended to individuals of similar problems.

Objectives

The objective of the present pilot study is to investigate if the WBVT is able to improve the muscle strength, functional abilities, postural control, and bone mineral density in children/adolescents with SMA type III.

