Null hypotheses to be tested:

1. That there is no statistically significant difference in gross motor function as measured using the North Star Ambulatory Assessment (NSAA) pre- and post-intervention.
2. That there is no statistically significant difference in functional abilities as measured using Pediatric Evaluation of Disability Inventory (PEDI) pre- and post-intervention.
3. That there is no statistically significant difference in postural control as measured using Segmental Assessment of Trunk Control (SATCo) pre- and post-intervention
4. That there is no statistically significant difference in sub-maximal exercise capacity as measured using the 2-minute walk test (2MWT) pre- and post-intervention.
5. That there is no statistically significant difference in body composition and bone mineral density as measured using dual X-ray absorptiometry (DXA) pre- and post-intervention.

Methodology

This feasibility study aims to examine the safety of the WBVT on children with type III SMA.

Children with type III SMA are targeted as they have adequate independence living in the community but still experience early fatigue during normal level of exercises due to the nature of their condition. They are at high risk of suffering from complications due to compromised mobility such as osteopenia, early loss of ambulation when compared with their healthy peers.

Intervention protocol

The WBVT will be performed on the Galileo™ Med L Plus (Novotech Medical GmbH) with the study participants standing with both knees flexed at least 20 degrees. The vibration frequency and duration will be increased over 5 days to the maximum of 3 minutes of 24 to 25 Hz with a peak to peak amplitude of 4mm. The participants of the intervention group will undergo the WBVT 1 session per day, 3 days per week for 4 weeks. The whole WBVT session will last 18 minutes with 9 minutes of vibration. This intervention regime is based on the recommended dosage to improve bone mineral density in children with physical disabilities in a systematic review on previous relevant literature (Matute-Llorente et al 2014). The intervention regime is as follows:

Day	Vibration 1	Rest 1	Vibration 2	Rest 2	Vibration 3	Rest 3
1st	1 min; 12Hz	3 min	1 min; 12Hz	3 min	1 min; 15Hz	3 min
2nd	1 min; 15Hz	3 min	1 min; 15Hz	3 min	2 min; 15Hz	3 min
3th	2 min; 15Hz	3 min	3 min; 15Hz	3 min	3 min; 15Hz	3 min
4th	2 min; 24-25Hz	3 min	2 min; 24-25Hz	3 min	2 min; 24-25Hz	3 min

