>5th	3 min; 24-25Hz	3 min	3 min; 24-25Hz	3 min	3 min; 24-25Hz	3 min

The participants will perform mini-squats (knee flexion from 20 to 40 degrees) during Vibrations 1 and 3 and weight-shifting between right and left legs during Vibration 2 on the vibration platform under the supervision of a research assistant, who will be trained by the PI prior to the commencement of the study. All treatment sessions will be conducted at the Hong Kong Polytechnic University Rehabilitation Clinic as most of children and adolescents with SMA study in main-stream schools in Hong Kong.

Participants:

10 children with type III SMA aged from 6 to 18 years will be recruited. The age range is extended aiming to increase the number of recruitment due to the rarity of the condition. All participants will continue their usual intervention regime, if any, during the study period. They are strongly encouraged not to participate any activities that may involve any total body vibration during the study period.

Inclusion criteria:

To be included in the study, children must:

1. Be able to stand on the vibration platform without support;
2. Be able to undertake clinical examination and DXA evaluation; and
3. Informed consent by the participant’s parent/ guardian.

Exclusion criteria:

1. There is a history of fracture within 8 weeks of enrolment of the present study and acute thrombosis, muscle or tendon inflammation, renal stones, discopathy or arthritis as reported by

their parent/ guardian.

2. There is a history of using any of the following medications, regardless of dose, for at least 1 month, within 3 months of enrolment into the present study: anabolic agents or growth hormone.

Outcome measures:

Assessments will be performed at baseline and after 4 weeks of the intervention. All outcome measures will be conducted on all study children, unless specified to children with specific diagnoses. They include:

1. Muscle strength

a) hand-held dynamometer will be used to measure muscle strength in hip flexors, hip extensors, hip abductors, knee extensors, knee flexors, ankle plantarflexors and dorsiflexors in standardised muscle testing positions (Clarkson and Gilewich 2000). Muscle strength will be reported in kilograms.

2. Functional abilities

a) North Star Ambulatory Assessment (NSAA) will be used to examine the gross motor function of the participants (Mayhew et al 2011, Scott et al 2012).

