b) 2-minute walk test (2MWT) will be used to assess submaximal exercise capacity (Pin 2014, Pin and Choi 2016). Distance covered in 2MWT will be measured by a distance-measuring trundle wheel in metres.

c) Range of movements in hip flexion, extension and abduction, knee flexion and extensions and ankle dorsiflexion and plantarflexion will be measured in standardised positions (Clarkson and Gilewich 2000).

d) Segmental Assessment of Trunk Control (SATCo) to assess the segment trunk control (Butler et al 2010).

e) Pediatric Evaluation of Disability Inventory (PEDI) (Haley et al 1992) to assess functional capacities in the domains of daily activities, mobility and social/cognitive function. A validated Chinese version will be used (Chen et al 2009).

3. Bone mineral density

a) Dual Energy X-ray Absorptiometry (DXA)- bone mineral content (BMC) and areal bone mineral density (aBMD) of the distal femur and total body will be measured. *Only if* it is not feasible to obtain the BMC and aBMD of the femur, BMD of the lumbar spine will be used. The effective radiation dose for these DXA studies will be <2 microSv, which is a very minimal dose of radiation (Houlihan and Stevenson 2009). All participants will have DXA done in a private service as bone density examination is not routine for the children with motor disabilities in Hong Kong.

b) Anthropometry at baseline and 4 weeks including standing height and weight. Body mass index (BMI) will be calculated and converted into a z-score.

4. Parental satisfaction

a) Parental/ participant questionnaire to record present medications of their children, satisfaction or comments on the intervention regime by children/ parents of the intervention group.

b) Visual analogue scale of 0 to 10, in which 0 means no pain and 10 as extreme pain to assess pain or discomfort at rest and if any, pain or discomfort associated with the intervention as reported by the children and/or parents.

c) A log of compliance and comments during the intervention.

Statistical analysis plan

Due to the small sample size, non-parametric tests will be used to analyse the results. All results will be reported in means and standard deviations. Wilcoxon Signed test will be used to

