compare all the outcome measures listed above (no. 1 to 3) before and after the intervention. Results of outcome measure no. 4 listed above will be reported in descriptive terms for the comments from the parents and/or from the participants and compliance/ comments during the intervention and Wilcoxon Signed test will also be used to compared the visual analogue score of discomfort before and after the intervention.

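### The bone objective is causal, but a 4-week before-after DXA comparison in one uncontrolled group of 10 children cannot show or exclude an effect of vibration

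*Combined protocol and SAP*

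**What the plan says.** All references are to the combined protocol and SAP.

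- **Objectives:** the study is to "investigate if the WBVT is able to improve the muscle strength, functional abilities, postural control, and bone mineral density" in children and adolescents with SMA type III.
- **Abstract:** "The outcomes also provide research evidence to clinicians if this intervention should be recommended to individuals of similar problems".
- **Null hypotheses, no. 5 (H5):** there is "no statistically significant difference in body composition and bone mineral density as measured using dual X-ray absorptiometry (DXA"), comparing before with after the intervention.
- **Participants:** "10 children with type III SMA aged from 6 to 18 years will be recruited". The term intervention group is used in places, but no second group, randomisation or run-in is described. Usual treatment continues.
- **Intervention protocol:** the children do mini-squats and weight-shifting on the platform during the vibration periods.
- **Outcome measures, 3(a):** "bone mineral content (BMC) and areal bone mineral density (aBMD) of the distal femur and total body will be measured", with lumbar spine as a fallback for the femur.
- **Outcome measures, 3(b):** "Anthropometry at baseline and 4 weeks including standing height and weight". A z-score is planned for BMI; none is stated for bone.
- **Statistical analysis plan:** the signed-rank test is used to "compare all the outcome measures listed above (no. 1 to 3) before and after the intervention". Results are given as means and SDs. There is no confidence interval, no covariate, and no statement on how a bone result may be read.

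**The concern.** The question asked and the quantity tested do not match. The Objectives ask what the therapy does to bone. The test asks whether the typical 4-week change differs from zero. In one treated group of growing children, that change is the sum of several things: any effect of vibration, growth, the exercise done on the platform, and whatever usual treatment contributes. Nothing in the plan separates them.

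Both possible results can therefore be misread. A significant gain could be reported as a bone benefit of vibration. A non-significant result could be reported as no bone effect, when ten pairs of scans 4 weeks apart may simply be too imprecise to tell. Bone mineral density is in the study title and has its own hypothesis, and the Abstract points the results at clinicians' recommendations, so either misreading would matter.

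**Working it through.** **No figure to reproduce.** The plan gives no alpha, power, SD, scan precision or bone accrual rate.

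**Inputs.** From the documents: n = 10, a 4-week interval, signed-rank test. Assumed:
- two-sided alpha 0.05;
- normally distributed changes;
- scan CV 1–3%;
- SD of the paired change = √2 × CV, so 1.41% at CV 1% and 4.24% at CV 3%. This counts scan error only. Real variation between children would make it larger.

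**Size of the test.** For n = 10 the exact test rejects when the smaller rank sum is 8 or less. There are 25 of 2¹⁰ = 1,024 sign patterns in each tail, so the size is 2 × 25/1,024 = 0.0488.

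**If H5 is not rejected.** 95% half-width = t(9; 0.975) × SD/√10, with t = 2.262:
- CV 1%: 2.262 × 1.414/3.162 = 1.01%
- CV 3%: 2.262 × 4.243/3.162 = 3.04%

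By simulation, 80% power needs a true change of about 1.02 SD: 1.02 × 1.414 = 1.44% at CV 1%, and 1.02 × 4.243 = 4.33% at CV 3%. Smaller true changes would often be missed.

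**If H5 is rejected: the growth part alone.** Four-week drift = annual gain × 28/365.25. Simulated total rejection with no effect of vibration or of any other source:

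| Assumed gain per year | 4-week drift | CV 1% | CV 3% |
|---|---|---|---|
| 1% | 0.08% | 5.2% | 4.9% |
| 3% | 0.23% | 7.2% | 5.2% |
| 6% | 0.46% | 14.6% | 5.9% |
| 12% | 0.92% | 43.5% | 9.1% |

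The excess over 4.9% is almost all false gain. At 1–3% a year it is negligible to small. It becomes large only with fast accrual and a precise scan together. The one relevant statement in the documents, "Osteopenia is common for this population group due to poor bone growth and muscle disuse", points towards the low end.

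**The other parts.** The exercise and usual treatment cannot be sized from the documents. They remain mixed with vibration even if growth is zero.

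**Would testing bone Z-scores solve it?** Suppose, as an assumption, that the children gain 1% a year while the reference population gains 6%. The adjusted change then drifts by −5% × 28/365.25 = −0.38%.
- False loss alone is 4.4% (CV 3%) to 11.2% (CV 1%), against about 2.4% nominal. The raw test in the same setting rejects about 5% in total.
- For a true 2% gain at CV 1.5% (SD 2.12%), the standardised shift is (2 + 0.08)/2.12 = 0.98 for the raw test and (2 − 0.38)/2.12 = 0.76 for the Z-score test. Power falls from 77% to 56%, before any height measurement error.

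**The case against.** The strongest defence is that this is a small feasibility study. Its title says so, the Abstract calls it a pilot that may show benefit, and the Methodology gives safety as an aim. H5 is worded only as a before-after difference, and the signed-rank test addresses exactly that. Lack of a control group also limits hypotheses 1 to 4, so bone is not unique. All of this stands. An uncontrolled pilot is legitimate and the H5 test is not invalid. What it does not answer is the causal wording of the bone objective, or the absence of any sentence limiting how the bone result is read.

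Two stronger readings are tempting, and the documents support neither.

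- **That growth will probably produce a false positive.** Over 4 weeks the drift may be small beside scan error, and the Abstract describes poor bone growth. The high rejection rates need inputs that the documents do not give.
- **That the defect is the missing bone Z-score, and a Z-score test should be required.** Z-scores remove expected growth only. They leave exercise and usual treatment in the change, and they can tilt the result towards false loss if these children accrue more slowly than the reference. A suitable reference for each site is also not given in the documents.

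The lumbar spine fallback is a matter of missing detail. It reads naturally as a decision for each child, and reporting by site settles it.

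**Conclusion.** The point holds as a mismatch between the bone objective and what the analysis can support. Neither rejection nor non-rejection of H5 is evidence about an effect of the therapy on bone. The attribution part follows from the design and needs no assumed figure. The precision part (half-width about 1.0–3.0%; 80% power only for changes of about 1.4–4.3%) rests on an assumed CV of 1–3% and on scan error as the only source of variation. The growth part is probably small, at about 5–7% rejection for an assumed 1–3% a year, and its true size cannot be determined from the documents.

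This should be changed, because it alters what the trial may conclude about an outcome named in its title. It does not affect the safety or feasibility results.

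**What to change.** 1. In the Objectives and in H5, reword the bone part as descriptive or as a feasibility aim, and bring the Abstract's sentence on recommendation into line for bone. Add to the Statistical analysis plan that a 4-week DXA change, or lack of change, in this single group is not evidence for or against a bone effect of WBVT.
2. In the Statistical analysis plan, report the paired change in BMC and aBMD, separately by DXA site, with a 95% confidence interval beside the means and SDs. Label any signed-rank p-value exploratory.
3. Optional: where a suitable paediatric reference exists for the site, describe the change in age-, sex- and height-adjusted Z-scores as a sensitivity description. It should not be a required test.

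**Cost.** Items 1 and 2 are text and reporting changes using scans already planned, with no new visit or measurement. Item 3 needs a reference to be found but uses the height already collected. The real price is that the bone result carries a weaker claim. A claim of effect would need a concurrent control.

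### Total-body bone mineral is analysed with no exclusion of the head, which modestly weakens aBMD and percentage BMC change in a trial of standing vibration (minor)

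*Combined protocol and SAP*

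**What the plan says.** Outcome measures, item 3(a), sets the DXA regions: "bone mineral content (BMC) and areal bone mineral density (aBMD) of the distal femur and total body will be measured". The only alternative region is a substitute for the femur: if "it is not feasible to obtain the BMC and aBMD of the femur, BMD of the lumbar spine will be used". The head, a sub-total region and total body less head are mentioned nowhere.

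Hypothesis 5 names no region. It tests for "no statistically significant difference in body composition and bone mineral density as measured using dual X-ray absorptiometry (DXA) pre- and post-intervention". The statistical analysis plan uses the Wilcoxon signed test to "compare all the outcome measures listed above (no. 1 to 3) before and after the intervention", so the total-body measures are formally tested. It adds that "All results will be reported in means and standard deviations", without saying whether change is absolute or percentage.

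Under Intervention protocol, vibration is given "with the study participants standing with both knees flexed at least 20 degrees", with mini-squats and weight-shifting between the legs. The sample and timing are: "10 children with type III SMA aged from 6 to 18 years will be recruited" and "Assessments will be performed at baseline and after 4 weeks of the intervention". The scans are done by a private service whose scanner and software outputs are not described.

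**The concern.** The load enters through the feet of a standing child, so a bone effect would be expected mainly in the legs, pelvis and spine. A total-body measure that includes the head averages in bone that this exercise has little reason to change. If the head's share of bone mineral varies with age, the amount averaged in also differs between a 6-year-old and an 18-year-old, and the ten children's percentage and aBMD changes would then differ partly through body proportions.

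What is at stake is sensitivity. Hypothesis 5 looks for a bone change over 4 weeks in 10 children, and such a test has little to spare. An unnamed region also leaves the choice to the scanning service, or to the analyst after the results are seen. A region that differed between visits would directly damage a before-after comparison without a control group.

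**Working it through.** **Inputs from the documents.** n = 10; ages 6 to 18; baseline and 4 weeks; paired Wilcoxon signed test; BMC and aBMD at distal femur and total body. The plan gives no effect size, SD, alpha, power or head share, so it has no figure to reproduce.

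**Assumptions.** The head does not change over 4 weeks. The head holds a share *h* of total-body BMC (10% to 40%) and a share *a* of projected bone area (8% to 20%). Two-sided alpha is 0.05. The standardised change below the head is *d* = 1.0. Changes are normally distributed.

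**Step 1: what an unchanged head does to each measure.**
- BMC in grams: total change = change below the head + 0. Nothing is lost.
- BMC in percent: total % change = (1 − *h*) × % change below the head. A 2% gain becomes 0.90 × 2% = 1.8% at *h* = 10%, and 0.60 × 2% = 1.2% at *h* = 40%.
- aBMD, absolute, with areas unchanged: total change = (1 − *a*) × change below the head. The part retained is 0.92 at *a* = 8% and 0.80 at *a* = 20%.

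**Step 2: power.** The test at n = 10 rejects when the smaller rank sum is 8 or less (true size just under 5%). By simulation, *d* = 1.0 gives about 79% (repeated runs fall between 78% and 79%). The effect of including the head in BMC depends on how measurement error behaves.

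(i) *Noise shrinks with the signal*, as when variation is mainly in how much each child responds. Then *d* = (1 − *h*)/(1 − *h*) = 1.0, and power is unchanged.

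(ii) *Independent errors of equal relative size in head and body.* Then *d* = (1 − *h*)/√[(1 − *h*)² + *h*²]:

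| *h* | *d* | Power |
|---|---|---|
| 10% | 0.9/√0.82 = 0.994 | 78% |
| 20% | 0.8/√0.68 = 0.970 | 76% |
| 30% | 0.7/√0.58 = 0.919 | 71% to 72% |
| 40% | 0.6/√0.52 = 0.832 | 63% |

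(iii) *Relative error of the total equals that of the body alone.* Then *d* = 1 − *h*. At *h* = 20%, *d* = 0.80 and power is about 60%. With head and body errors of equal relative size, this needs them to be perfectly correlated. With independent errors, the head's relative error would have to be √(1 − 0.8²)/0.2 = 0.6/0.2 = 3 times the body's.

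**Step 3: noise in BMC in grams.** If independent head error has an SD of *f* times the SD below the head, *d* = 1/√(1 + *f*²). For *f* = 0.25, 0.5 and 1.0 this gives *d* = 0.970, 0.894 and 0.707, and power of about 76%, 69% and 50%. Model (ii) is the case *f* = *h*/(1 − *h*); at *h* = 20%, *f* = 0.25, and both routes give 76%.

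**The case against.** The strongest reply is that the documents never say the head is included. That is correct: inclusion is the ordinary meaning of total body, not a statement in the plan. The head's share, its lack of response, any change of that share with age, and the availability of a head-excluded region are likewise absent from the documents. The size of the effect therefore has to stay a range under assumptions.

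A reader might infer that any skeletal change is diluted. The algebra does not support this. An unchanged head cancels from each child's paired BMC difference in grams, and the plan does not say that percentage change will be used.

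A reader might also take the fall from 79% to 60% as the cost. That figure needs the least favourable of the three error models. At the same 20% share, independent errors of equal relative size cost about 3 points. The starting effect of 1.0 is itself an assumption, and a generous one for 4 weeks.

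Finally, a loaded site, the distal femur, is also measured, so the bone question does not rest on total body alone. This stands and lowers the importance of the point. It does not remove it: the plan itself foresees children whose femur cannot be scanned and offers the lumbar spine only as a substitute there, and total body is tested in its own right.

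**Conclusion.** The point holds as a minor one. The analysed total-body region is unqualified, ordinarily includes the head, and fits poorly with a load delivered through the legs. If the head does not respond, absolute aBMD change is retained at 92% to 80% (assumed area share 8% to 20%), and percentage BMC change at 90% to 60% (assumed BMC share 10% to 40%). BMC change in grams keeps its full size but may carry extra noise. The loss of power ranges from nil to about 19 points at a 20% share, according to the error model, and the documents do not show which model applies.

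A reader might infer a bias or a false positive risk. The documents do not support that: each child is their own control over 4 weeks, the head share is nearly constant within a child over that time, and a zero change stays zero after multiplication by (1 − share). The feasibility and safety conclusions are not affected.

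**What to change.** In item 3(a) and hypothesis 5, make total body less head BMC and aBMD the analysed total-body measure, where the DXA service's software reports it. In the same place:

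- require the same region definition at baseline and 4 weeks for every child;
- state whether change is analysed in absolute units or as a percentage;
- report whole-body values with the head descriptively, without a test.

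If the service cannot report the sub-region, state that total body includes the head, and interpret aBMD and percentage BMC change accordingly.

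The cost is an edit to the text and one enquiry to the private DXA service before the first scan. If the sub-region is available from the planned scan, no further scan or radiation is needed. The one thing given up is a formal test on the whole-body values.

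### A ten-child pilot lists five formal null hypotheses and about 28 significance tests, with no significance level, primary outcome, multiplicity rule or exploratory label

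*Combined protocol and SAP*

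**What the plan says.** The title, Abstract and Methodology present a pilot or feasibility study, and the Methodology says: "This feasibility study aims to examine the safety of the WBVT on children with type III SMA". The Objectives section, however, poses only an efficacy question: whether the therapy can "improve the muscle strength, functional abilities, postural control, and bone mineral density in children/adolescents with SMA type III".

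Under "Null hypotheses to be tested" the protocol sets out five hypotheses, on NSAA, PEDI, SATCo, the 2-minute walk test and DXA. Each is worded in terms of statistical significance before and after the intervention. The fifth reads "no statistically significant difference in body composition and bone mineral density as measured using dual X-ray absorptiometry (DXA").

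The Statistical analysis plan applies the Wilcoxon test to "compare all the outcome measures listed above (no. 1 to 3) before and after the intervention", and its last sentence adds the visual analogue score. The only planned summary is means and standard deviations. No section gives a significance level, sidedness, a primary outcome, a multiplicity rule or an exploratory label for the tests.

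On use of the results, the Abstract first hedges ("It is anticipated that the outcomes of this pilot study for SMA may show if this intervention is safe, feasible and beneficial") and then states: "The outcomes also provide research evidence to clinicians if this intervention should be recommended to individuals of similar problems".

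**The concern.** A study that lists formal hypotheses has to say what would reject them, or say that the tests are exploratory. This plan does neither. Since no intervals or effect estimates are planned, the p-values are the only stated inference, and there are many of them. One isolated p-value below 0.05 could be reported as benefit and passed to clinicians under the Abstract's statement on recommendations.

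The hypotheses also have gaps that do not depend on multiplicity:

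- The PEDI hypothesis covers three domains and the DXA hypothesis several variables, with no rule on how many must change.
- Body composition, named in the DXA hypothesis, corresponds to no variable listed under Outcome measures.
- Muscle strength comes first in the objective and first among the outcomes, but has no hypothesis.

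**Working it through.** The plan states no error rate, so there is no figure of its own to reproduce.

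**Number of tests**, counted from Outcome measures and the Statistical analysis plan:

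| Measure | Variables |
|---|---|
| Strength ("hip flexors, hip extensors, hip abductors, knee extensors, knee flexors, ankle plantarflexors and dorsiflexors") | 7 |
| NSAA | 1 |
| 2-minute walk test | 1 |
| Range of movement | 7 |
| SATCo | 1 |
| PEDI domains | 3 |
| DXA (BMC and aBMD at two sites) | 4 |
| Height, weight, BMI z-score | 3 |
| Visual analogue score | 1 |
| **Total** | **28** |

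The text leaves room for other counts:

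- 28 − 2 = 26 if height and weight only feed the BMI z-score.
- 28 + 14 = 42 if strength and range of movement are analysed by side.
- 28 − 1 = 27 if lumbar-spine BMD (one variable) replaces the two femur variables in every child.
- Any body-composition variable would add to these.

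**Level of one test.** Assume two-sided 0.05 and no true change. The exact signed-rank test with 10 non-zero, untied differences rejects when the smaller rank sum is 8 or less. Its level is 50/1024 = 0.0488, or 25/1024 = 0.0244 in the favourable direction. With 8 or 9 non-zero differences the level is 40/1024 = 0.0391.

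**Average number of false positives** (does not depend on correlation):

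- 28 × 0.0488 = 1.37, about 1.4.
- 28 × 0.0391 = 1.09, about 1.1.
- 26 × 0.0488 = 1.27; 42 × 0.0488 = 2.05.
- Leaving out height, weight and BMI z-score: 25 × 0.0488 = 1.22.

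**Chance of at least one false positive over 28 tests.** Independent: 1 − (1 − 0.0488)^28 = 0.754. The figures at a common correlation are simulated with normal differences and 10 pairs: about 65% at 0.3, 54% at 0.5 and 38% at 0.7. Repeat runs differed by one or two percentage points.

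**Chance of at least one false improvement over the 25 variables** (the visual analogue score included). Independent: 1 − (1 − 0.0244)^25 = 0.461. Simulated: 33%, 26% and 18% at correlations 0.3, 0.5 and 0.7. A single test has 2.4%.

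**Hypotheses with several variables.** If any one variable, in either direction, may reject:

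- PEDI: 1 − (1 − 0.0488)^3 = 0.139.
- DXA: 1 − (1 − 0.0488)^4 = 0.181.

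Both assume independence and are lower under positive correlation.

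**Sensitivity to the assumed level** (28 independent tests at the nominal level). At 0.01: 28 × 0.01 = 0.28 expected and 1 − 0.99^28 = 24.5% for at least one. At 0.10: 2.8 expected and 1 − 0.90^28 = 94.8%.

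**The case against.** The strongest reply is that this is a pilot in a convenience sample of 10. It says so throughout, and a pilot need not control family-wise error. That stands: the absence of a correction is not in itself the fault. But the pilot label describes the study, not its tests, and it sits beside formal hypotheses, an efficacy objective and the Abstract's sentence on recommendations.

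Second, the size is easily overstated. A reader might infer from a mean of 1.4 that the plan is almost bound to yield a chance finding. It is not. Correlated outcomes make false positives cluster, and at a correlation of 0.7 most trials with no true change would show none. The 1.4 also assumes no zeros or ties on any variable, although zero differences are plausible on ordinal scores and a pain scale. And it counts height and weight as unchanged, when growth alone can move them.

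Third, not all 28 are efficacy variables. The visual analogue score records pain at rest and pain with the intervention, so it measures tolerability, and including it slightly inflates the false-improvement figures.

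Finally, a reader might infer that the five hypotheses are cut off from the analysis. They are not: every instrument they name is tested. The mismatch is confined to the gaps set out above.

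**Conclusion.** The concern holds as a gap in labelling and decision rules, and it should be fixed. The plan tests about 28 variables (26 to 42, depending on reading) with no stated basis for calling any result significant. Two of its five hypotheses cannot be decided as written.

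On the 28-variable reading the average is 1.1 to 1.4 false positives, with a 38% to 75% chance of at least one over correlations 0.7 to 0. The chance of at least one false improvement is 18% to 46%, against 2.4% for a single test. These figures rest on an assumed two-sided 0.05, no true change, and the stated numbers of non-zero, untied differences. The correlations are illustrative, because the documents give none.

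The documents do not support the stronger conclusions that a false finding is near certain or that this pilot had to adjust for multiplicity.

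**What to change.** Change wording in the protocol and Statistical analysis plan only:

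1. Label all efficacy tests exploratory and hypothesis-generating. Report each outcome as the paired change with a 95% confidence interval (for example Hodges-Lehmann), state that the intervals are not adjusted for multiplicity, and claim no significance.
2. Alternatively, name one efficacy outcome already collected (the sponsor's choice) for a single exact two-sided 0.05 test, and treat the rest as in item 1. This test can reject only with at least 6 non-zero differences: with 6, the smallest p is 2/64 = 0.031.
3. Report height and weight descriptively as growth, and the visual analogue score descriptively as tolerability.
4. Reword the Abstract's sentence on recommendations to say that efficacy results from this uncontrolled pilot can only inform a later trial.
5. State the PEDI score for the second hypothesis and the DXA variable for the fifth, including how the lumbar-spine fallback is handled. Tie body composition to a variable or remove it. Add muscle strength to the hypothesis list or explicitly exclude it.

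Bonferroni over 28 is not workable: 0.05/28 = 0.00179 is below the smallest attainable two-sided p with 10 pairs, 2/1024 = 0.00195.

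No new data or visits are needed. The downside is fewer outcomes on which significance can be claimed. The change does not make an uncontrolled before-after difference attributable to the intervention; it only stops chance findings being presented as tested results.
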